4.8 Methods to Be Used For Handling Missing Data

All available data will be included in data listings and tabulations. Imputed dates will not be included in the listings.

No imputation of missing data is planned for safety endpoints and PK endpoints. If outliers are detected, a robustness analysis where the outlier effect is reduced or eliminated may be considered.

Missing data for tumor response related variables will be handled/imputed in accordance with the RECIST criteria version 1.1^2 and for subjects with ovarian cancer according to RECIST 1.1 in combination with CA-125 as defined by the Gynecological Cancer Intergroup³.

TPL N°: eTPL SA-02-01 TPL Version: 02 Of SOP SA-02.08

OF SOP SA-02.08

TPL Effective Date: 31 Mar 2016

Approved in Vault: 6/30/2021

For the expansion part, imputation methods might be introduced in case of incomplete tumor assessments for the analysis of the sum of diameters (SOD) and documented in a SAP amendment.

4.9 Changes to Protocol

Changes compared to protocol final version 10.0, dd. 9 December 2019:

Table 4 Evaluation of Response in section 15.1 of this SAP has been updated by clarifying the definition of not-evaluable (NE).

Subgroup analysis for Cohort 2 (up to 2 lines of prior therapy versus more than 2 lines of prior therapy within the 2.2 mg/kg dose level), Age (age<65 years and age ≥65 years), Gender, Histology: squamous versus non-squamous, ECOG performance score (0 versus 1), smoking status ((current smoker, past smoker, non-smoker), amendment 6 period (inclusion before amendment 6, after amendment 6), best response to latest regimen (CR, PR, SD, PD) and histology results (Chondrosarcoma vs other) – Cohort 5 are added.

IRC tumor assessments are not presented, the BOR and CBOR based on IRC are listed only.

PSA results (when available) and urinalysis results will only be listed.

The Safety Set is updated by removing the condition to have a valid post-baseline safety assessment as it is considered appropriate to keep all exposed subjects in the safety set to align with ICH guidelines.

Additional adverse events tables are added for completeness.

One additional analysis set is added: PK analysis set.

The interim analysis at the end of the dose-escalation part is removed as data from the dose-escalation and expansion part will be presented together as described in section 4.2.

5. Trial Subjects

5.1 Disposition of Subjects

Screening failures including failure reason and re-screening information will be presented in a listing. Subjects screened but never started trial treatment will be included in the same listing. The number of screen failure and the screen failure reasons will be tabulated.

The number of subjects in each analysis set as defined in section 4.3 will be tabulated. The reason(s) for subjects not included in each population will be presented in a listing.

The frequency of subjects treated, of subjects who discontinued the trial treatment and of subjects who terminated the trial will be given for the full analysis set (FAS). The primary reason for discontinuation of the trial treatment and terminating the trial will be summarized. The details of the 'other reason' will be included in the listing.

Subject dispositions will also be presented in flow diagrams in accordance with the current CONSORT statement¹.

5.2 Protocol Deviations

The important major protocol deviations will be summarized. The details will be listed.

In addition, Covid-19 related PDs will be listed separately:

All important PDs related to Covid-19;

TPL N°: eTPL SA-02-01 TPL Version: 02

Of SOP SA-02.08
TPL Effective Date: 31 Mar 2016
Approved in Vault: 6/30/2021

- All non-important PDs related to Covid-19 (this will be major, non-important as well as minor, non-important);
- Subject listing of missed/changed visits;
- Subject listing of assessments missed due to visits impacted by Covid-19.

A summary table of the above might be added to evaluate the impact of Covid-19.

Protocol deviations will be defined in the protocol deviations plan.

5.3 In- and Exclusion Criteria

Listing of all in- and exclusion criteria not met as completed on the "Inclusion/Exclusion criteria not met" page of the eCRF will be provided.

Information of informed consent will be presented in the disposition listing.

6. Demographic Characteristics

Descriptive statistics with respect to subject characteristics at baseline will be displayed for the FAS.

The variables to be summarized are:

- Gender (Male/Female)
- Age (years, continuous and categorical: age<65 years and age ≥65 years)
- Race (White, Black or African American, Native Hawaiian or other Pacific Islander, Asian, American Indian or Alaska native, Other)
- Ethnic origins (Hispanic or Latino, Not Hispanic or Latino)
- Region (US, Europe)
- Weight (kg)
- Height (cm)
- BMI (kg/m²)
- HbA1c
- Smoking history
 - Usage (Current smoker, Past smoker, Non-smoker)
- Drinking history
 - Usage (Daily, 3-6 times per week, 1-2 times per week, Less than 4 times per month, None)
- Contraception data
 - Subject considered as sterilized or infertile (Yes, No)
 - Reason (Surgical sterilization, Postmenopausal, Other)
- Contraception details (listed only)
 - Subject practice adequate contraception (Yes, No)

Page 17 of 46

TPL N°: eTPL SA-02-01

TPL Version: 02

Of SOP SA-02.08 TPL Effective Date: 31 Mar 2016

Page 18 of 46

Type of contraception (Pills, Implant, Vaginal device, Injections, Transdermal patches, Other)

Details of the other categories mentioned above will be added to the listings.

7. Baseline Disease Characteristics

Descriptive statistics with respect to subject disease characteristics at baseline will be displayed for the FAS.

The variables to be summarized are:

- ECOG performance score (0-5). Note: at entry only subjects with an ECOG performance score of 0 and 1 are allowed)
- Cohort 2: up to 2 treatment lines of prior therapy versus more than 2 treatment lines of prior therapy within 2.2 mg/kg group
- Lactate dehydrogenase (LDH) for melanoma subjects only
- % AxI-positive tumor cells (%>=1+) Expansion part only
- Type of cancer at initial diagnosis (NSCLC, Follicular or Hürthle cell thyroid cancer, Papillary thyroid cancer, Medullary thyroid cancer, Anaplastic thyroid cancer, Ovarian cancer, Cervical cancer, Endometrial cancer, Melanoma, and other primary sites as per enrolment in the expansion part)
- Tumor stage at initial diagnosis (I, IA, IB, II, IIA, IIB, III, IIIA, IIIB, IV, IVA, IVB, IVC) by indication.
- Tumor stage at screening (I, IA, IB, II, IIA, IIB, III, IIIA, IIIB, IV, IVA, IVB, IVC) by indication.
- Histological results (see CRF for the details) by indication
- Histological subtype (see CRF for the details) by indication
- Mutational status (EGFR mut, ALK rearrangement, BRAF, NRAS, None) and mutational sub-term (T790M, L858R, ...) combined
- Time (in years) from initial diagnosis to start date of IMP administration (continuous and in classes: <1 year, 1-<2 years, 2-<3 years, 3-<4 years, 4-<5 years, >=5 years)
- Snellen score (OD and OS)
- Number of metastatic sites per subjects (1, 2, 3, 4, >=5)
- Number of subjects with CNS metastases
- Number of subjects with liver metastases
- Sum of reference diameters of target lesions (mm)
- CA-125 as continuous and as categorical: <=ULN, >ULN (for Ovarian cancer subjects only)
- Tumor classification (TNM) at screening and initial diagnosis and histological grade will be listed only

Approved in Vault: 6/30/2021

Of SOP SA-02.08 TPL Effective Date: 31 Mar 2016

8. Biopsy Information

Descriptive statistics with respect to the biopsy information at baseline will be displayed for the FAS.

The variables to be summarized are:

- Biopsy performed (Yes, No) at screening*
- Type of biopsy (Fresh, Archived) at screening*
- Location of biopsy (multiple answers possible when different biopsies were done at screening)

Version: 4.0

- o Time since last biopsy before start of IMP to start date of IMP (months)
- Time since biopsy to start date of IMP (months) will be added in the listing for each biopsy performed (before or after the start date of IMP)
- Number of subjects with evaluable biopsies before first IMP administration and after (by visit)
- Reason for biopsy failure (by visit), listed only (free text)

Details of the other categories mentioned above will be added to the listings.

9. Medical and Surgical History

Medical conditions and surgeries will be coded using the Medical Dictionary for Regulatory Activities (MedDRA).

The medical conditions (separately for active (ongoing) and non-active conditions) and the surgeries will be tabulated separately, by system organ class (SOC) and preferred term (PT) for the FAS. Tables will be ordered by decreasing frequency of SOC and by decreasing frequency of PT within SOC. As mentioned in the section 17.2 of Adverse Events, the adverse events collected during the pre-treatment period will be tabulated together with the medical history.

All details will be listed.

10. Prior Cancer Therapies

Prior systemic cancer therapies will be summarized for the FAS as described below.

Prior systemic therapies in the metastatic setting will be listed and tabulated by first and fourth Anatomical Therapeutic Chemical class (WHO-DD dictionary, ATC 1 name and ATC 4 name) for the FAS. ATC classes will be ordered by decreasing frequency. In addition, the latest treatment line, the latest treatment line -1, the latest treatment line -2, and the latest treatment lines – (>=3) of prior cancer therapies will be tabulated in the same way to see what the subjects received just before entering the trial and earlier to see the influence on Axl expression.

Prior radiation therapies and prior surgeries will be coded using the Medical Dictionary for Regulatory Activities (MedDRA) and presented separately by system organ class and preferred term (ordered by decreasing frequency of SOC and by decreasing frequency of PT within SOC).

In addition, the number of prior treatment lines (not taking into account surgeries and radiation, restricted to systemic therapies in the metastatic setting) will be summarized by means of descriptive statistics and by category $(1, 2 \text{ and } \ge 3)$ and the best response to

TPL Version: 02

Page 19 of 46

TPL N°: eTPL SA-02-01 Of SOP SA-02.08 TPL Effective Date: 31 Mar 2016

Approved in Vault: 6/30/2021

^{*} independent if at screening or re-screening visit.

the latest treatment line, the latest treatment line -1, the latest treatment line -2, and the latest treatment lines -(>=3) of prior cancer therapy will be tabulated together with prior surgery related to cancer (Yes/No) and prior radiotherapy (Yes/No).

Version: 4.0

All details recorded in the eCRF will be listed.

11. Subsequent Cancer Therapies

Subsequent cancer therapies will be summarized for the FAS as described below.

Subsequent systemic cancer therapies in the metastatic setting will be listed and tabulated by first and fourth Anatomical Therapeutic Chemical class (WHO-DD dictionary, ATC 1 name and ATC 4 name) for the FAS. ATC classes will be ordered by decreasing frequency.

On-study radiation therapies and surgeries will be coded using the Medical Dictionary for Regulatory Activities (MedDRA) and presented by system organ class and preferred term. SOC and PT (within SOC) will be ordered by decreasing frequency.

All details will be listed.

12. Procedures

Non-protocol medical procedures will be coded using the Medical Dictionary for Regulatory Activities (MedDRA).

The medical procedures will be tabulated by system organ class (SOC) and preferred term (PT) for the FAS. Table will be ordered by decreasing frequency of SOC and by decreasing frequency of PT within SOC.

All procedures will be listed.

13. Prior and Concomitant Medications

Prior and Concomitant medications will be classified according to World Health Organization Drug Dictionary.

Medications will be reported according to the following two distinct categories:

- Prior when they start and end before the first day of trial treatment.
- Concomitant when they start before the first day of trial treatment and stop or continue after the first day of trial treatment, or when they start on or after first day of trial treatment.

The number and percentage of subjects receiving a concomitant medication will be displayed by first and fourth Anatomical Therapeutic Chemical class (WHO-DD dictionary, ATC 1 name and ATC 4 name) for the FAS. ATC classes will be ordered by decreasing frequency.

In addition, the concomitant medications for blood transfusions will be presented separately in the same way.

[figure not shown]
Prior medications will only be listed.

All medications recorded on the (prior and) concomitant medications eCRF page, classified as either prior or concomitant medication, will be listed separately. The listings will include details such as indication, dose, route, frequency, and start and stop dates. Also the specific AE or medical history event will be included where applicable.

TPL N°: eTPL SA-02-01 TPL Version: 02 Of SOP SA-02.08

TPL Effective Date: 31 Mar 2016

Approved in Vault: 6/30/2021

14. Primary Endpoint

Dose-escalation part

DLT analyses will be done on the dose-determining set (DDS) in the dose-escalation part of the trial.

Version: 4.0

The number of subjects with a DLT will be presented for each dose level and treatment schedule. In addition, a plot of the dose level by subject (in order of inclusion) will be presented marking the DLTs observed (see CRM examples in the protocol final version 10.0, dd. 9 December 2019, Appendix II) and also indicating the subjects which are not evaluable for DLT (not part of the DDS) for each treatment schedule.

Dose-escalation and Expansion part

The safety profile of enapotamab vedotin will be established based on the safety outputs mentioned in section 0.

15. Efficacy Evaluation

Efficacy results will be presented on the FAS unless specified otherwise.

15.1 Response

The response results from the dose-escalation part and the expansion part will be presented using summary statistics.

Response will be defined according to RECIST 1.1. For subjects with ovarian cancer (Cohort 7) the response will be defined on the combination of the response according to RECIST 1.1 and CA-125 (see below in section 15.1.2).

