## 10. STATISTICAL ANALYSIS

All statistical analysis will be performed by a Contract Research Organization (CRO) [REDACTED] under the direction of sponsor personnel. Any data analysis carried out independently by the investigator should be submitted to the sponsor prior to publication or presentation.

All data will be listed. Also, data will be summarized using descriptive statistics (continuous data) and/or contingency tables (categorical data) for demographic and baseline characteristics, efficacy measurements, safety measurements, and all relevant pharmacokinetic measurements.

The results will be presented by the 1Q3W, 3Q4W dose escalation and expansion parts separately. Also, the results will be presented by groups and total. In the dose-escalation 1Q3W and 3Q4W arms of the trial, groups are defined by dose-levels. In the expansion part, groups are defined by arm and dosing regimen. The results from the patients in the expansion part will be presented 2 times: by cohort and in total. In addition, for NSCLC patients without EGFR/ALK mutations, data will be summarized based on different dosing regimens, e.g., 1.8 mg/kg 1Q3W, 2.2 mg/kg 1Q3W. For the sake of the statistical analyses and summaries, baseline is defined as the available data from the latest recorded measurement made before the first enapotamab vedotin administration.

In general, in plots where patient data are grouped together (e.g., plots of means), the ticks on the time-axis will denote the nominal visit numbers (e.g., 0, C1V1, C1V2, C1V3 etc.) separated with distances proportionate to the difference between the time points of the corresponding visits in the relevant dose schedule (cf. the Visit Number and Day/Week rows of the assessment tables in Section 8). In plots where individual patient data are plotted vs. time, the time on the horizontal axis will denote the actual time since C1V1.

Details of statistical analysis and data reporting will be provided in a Statistical Analysis Plan (SAP) document finalized prior to database lock. Additional analyses may be added in the SAP and tables, listings and figures shells will also be provided.

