### 10.2.3 Expansion Part

The results from the expansion phase will be presented using summary statistics. For each cohort,

Document Name: GCT1021-01 Protocol

Document Number: TMF-03326

Version: 11.0

---

the number of responders will be evaluated. Let  $\pi_{response,i}$  denote the proportion of responders in cohort  $i$ , where  $i=1, 2, 3, 4, 5$  or  $6$ . The null hypothesis  $H_{0,i}: \pi_{response,i} \leq 0.10$  will be tested against the one-sided alternative hypothesis  $H_{alt,i}: \pi_{response,i} > 0.10$ , for Cohorts 1-6 and Cohort 8, using the exact binomial test on the 5% significance level, for both confirmed as well as unconfirmed response. The null hypothesis for the platinum-resistant ovarian cancer patients in Cohort 7  $H_{0,7}: \pi_{response,7} \leq 0.15$  will be tested against the one-sided alternative hypothesis  $H_{alt,7}: \pi_{response,i} > 0.15$ . Patients receiving different dosing regimens will be analyzed separately from each other.

With a minimum follow up of at least 7 months for all patients, the analysis per CSR cutoff is considered the full efficacy results. Any data collected after the CSR cutoff will be presented in data listings in the CSR addendum.

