## **10.4 Response**

Response in solid tumor cancers will be assessed in accordance with the RECIST criteria version 1.1 and for patients with ovarian cancer according to RECIST 1.1 in combination with CA 125 as defined by the Gynecological Cancer Intergroup.

Document Name: GCT1021-01 Protocol

Document Number: TMF-03326

Version: 11.0

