#### **10.4.1 Response Evaluation and Reporting of Results**

In the dose escalation, response evaluation will be performed by the investigator and sponsor. In the expansion, response evaluation will be performed by the investigator and sponsor as well as a group of external medical experts. Each patient will be assigned one of the following categories:

- 1) CR,
- 2) PR,
- 3) SD,
- 4) PD, or
- 5) Not Evaluable

Patients in response categories 1 and 2 are considered responders and patients in response categories 4 and 5 are considered as failing to respond to treatment (disease progression). Patients in response categories 1, 2 and 3 are considered to be in disease control.

Individual patient data listings and summaries of objective response, best overall tumor response (based primarily on confirmed but also on unconfirmed response) and disease control will be presented.

For patients with ovarian cancer, responses will be evaluated and reported as per RECIST 1.1, CA 125 and the combination of the two sets of response criteria in accordance with the Gynecological Cancer Intergroup definitions.

For patients with prostate cancer, responses will be evaluated and reported as per RECIST 1.1 and PSA according to the Updated Recommendations from the Prostate Cancer Clinical Trials Working Group 3.

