### 10.9.2 Expansion

Table 28. Impact of Sample Size on Descriptive and Inferential Statistics for Endpoints in the Expansion Part

The widths of the confidence intervals apply to binary endpoints of both safety (e.g., AE) and efficacy (e.g., response) nature.

For the test of the null hypotheses (cf. Section 10.2.3): e.g., assuming  $\pi_{response}=30\%$ , the probability of rejecting the null hypothesis  $H_0: \pi_{response} \leq 0.10$  is 69% when N=22.

The sample size in this exploratory trial has not been determined based on a formal power analysis. A power analysis of various assumptions of  $H_{0,i}$  and  $H_{alt}$  is presented in Table 29.

Document Name: GCT1021-01 Protocol

Document Number: TMF-03326

Version: 11.0

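### The readable SAP does not carry over the protocol's exact binomial test of response rate, states no interval for cohort-level ORR, and does not log the omission

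*SAP*

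**What the plan says.** Protocol 10.2.3 opens with "The results from the expansion phase will be presented using summary statistics" and then commits to a hypothesis test for each cohort. The null is a response rate of at most 10% in Cohorts 1-6 and 8, and at most 15% in Cohort 7, each against a one-sided alternative, "using the exact binomial test on the 5% significance level, for both confirmed as well as unconfirmed response". It adds: "Patients receiving different dosing regimens will be analyzed separately from each other". Protocol 10.4.1 ranks the two response versions: summaries are "based primarily on confirmed but also on unconfirmed response". Protocol 10 hands the detail on: "Details of statistical analysis and data reporting will be provided in a Statistical Analysis Plan (SAP) document finalized prior to database lock". It foresees that the SAP may add analyses.

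SAP 15.1 keeps the opening idea: "The response results from the dose-escalation part and the expansion part will be presented using summary statistics". The test does not follow. SAP 15.1.1 defines responders and confirmation in detail, without a null rate, a test or an interval. SAP 4 summarises categorical data as frequencies and percentages, and specifies 95% intervals only for time-to-event quantities. The table list (20.1) and the SAP addendum name neither a test nor a cohort-level ORR interval.

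The nearest thing to an interval is the forest plot of confirmed ORR by subgroup (SAP 4.4; Graph 14.02.01.01), for which no interval method or level is given. SAP 4.9 lists changes from protocol v10.0, including PSA and urinalysis becoming listing-only, but nothing about this test.

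**The concern.** The test is the protocol's only formal efficacy hypothesis test, and the expansion power figures are built on it. A programmer working from SAP 4 and 15.1 would produce counts and percentages only. Whether ORR exceeds the protocol's null would then not appear as a planned result, and the uncertainty of each cohort's rate would not be shown. If the p-value or interval is added later, its method and level would be chosen with the data in hand. That choice matters, because a one-sided 5% test and a two-sided 95% interval can disagree.

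The two omissions differ in kind. The missing test is a discrepancy between protocol and SAP. The missing interval is a gap in the SAP alone. Protocol 10.9.2 says "The widths of the confidence intervals apply to binary endpoints of both safety (e.g., AE) and efficacy (e.g., response) nature", but it says so as sample-size justification and does not promise a reported interval.

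**Working it through.** **Inputs.** One-sided 5% exact binomial test, p0 = 0.10 (Cohort 7: 0.15), from protocol 10.2.3. Maximum cohort sizes: 37 for Cohorts 1, 3, 4, 5, 7 and 8; 45 for Cohort 6; 82 for Cohort 2, of whom up to 30 at 1.8 mg/kg (protocol 3.4, Table 1).

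**Reproducing the plan's figure.** The rejection count r is the smallest r with P(X >= r | N, p0) <= 0.05. For N=22 and p0=0.10, P(X >= 5) = 0.0621 and P(X >= 6) = 0.0182, so r = 6. Power at 30% is P(X >= 6 | 22, 0.30) = 68.7%, against 69% in protocol 10.9.2. The Table 29 cells for N=22, 30, 37, 45 and 82 also reproduce within one point. The power figures therefore rest on exactly this test.

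**What the test and an exact interval would show at the smallest rejecting count.** Intervals are two-sided Clopper-Pearson.

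| Null | Count | ORR | One-sided p | 95% CI | 90% CI |
|---|---|---|---|---|---|
| 10% | 6/22 | 27.3% | 0.018 | 10.7-50.2% | 12.6-46.8% |
| 10% | 7/30 | 23.3% | 0.026 | 9.9-42.3% | 11.5-39.4% |
| 10% | 8/37 | 21.6% | 0.027 | 9.8-38.2% | 11.2-35.6% |
| 10% | 9/45 | 20.0% | 0.032 | 9.6-34.6% | 10.9-32.3% |
| 15% | 7/22 | 31.8% | 0.037 | 13.9-54.9% | 16.0-51.5% |
| 15% | 10/37 | 27.0% | 0.042 | 13.8-44.1% | 15.5-41.5% |

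One responder fewer does not reject: 5/22 against 10% gives p=0.062, and 6/22 against 15% gives p=0.100.

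**Test against interval.** In five of the six rows (all except 6/22) the test rejects while the 95% interval still contains the null. The 90% interval excludes the null in all six, because its lower limit is the one-sided 5% bound.

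**Interval width depends on the count.** At N=22 the 95% interval is 15.4 points wide at 0/22, 28.0 at 2/22 (the futility boundary for Cohorts 1-5) and 39.5 at 6/22.

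**Multiplicity if the test is run as the protocol states.** Assume nine independent strata at maximum size, with Cohort 2 split 30/52. The attained levels are 0.0274 for each of five strata at N=37 (Cohorts 1, 3, 4, 5 and 8), 0.0315 (N=52), 0.0258 (N=30), 0.0320 (N=45) and 0.0419 (Cohort 7, N=37). The chance of at least one rejection when every true rate equals its null is 1 - (0.9726^5 × 0.9685 × 0.9742 × 0.9680 × 0.9581) = 0.24. Nine tests at a full 5% would give 1 - 0.95^9 = 0.37. Both figures are for one response definition.

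**The case against.** The strongest reply is that silence cancels nothing. Protocol 10.2.3 specifies the test completely, 4.9 is where the SAP records departures, and it records none, so the test can be read as still in force. This stands. A reader might infer that the sponsor dropped the test, or that the efficacy question lost its pre-specification. The documents support neither, because the pre-specification is in the protocol. What remains is that the document governing the outputs does not produce the test.

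A second reply is that the evidence is incomplete. Section 4.9 compares with protocol v10.0, and only v11.0 is available. Protocol 10.2.3 itself carries Amendment 10 text on the reporting cutoff. The amendment summary does not mention adding the test, so it was probably in v10.0, but that cannot be confirmed. The table shells are not supplied, SAP 15.8 and 18 are blacked out, and an interval could sit in the shells. The subgroup forest plot would conventionally show intervals. All of this limits the claim to the readable SAP.

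A third reply is that the harm is small. Response is a secondary endpoint, protocol 10.9.2 calls the trial exploratory, development stopped in November 2020, and counts with denominators let a reader derive both quantities. This also stands. It limits the consequence to reporting and traceability, but does not remove the inconsistency.

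It is also tempting to say that 40 points of uncertainty go unreported at N=22. That width applies only near 6/22.

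**Conclusion.** The point holds as a protocol-SAP inconsistency on a secondary endpoint. The readable SAP does not implement the exact binomial test, gives no interval for cohort-level ORR and does not log the omission. The primary safety conclusions are unaffected.

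Its size is one planned p-value and one statement of precision per cohort and regimen. At N=22 the outcome against 10% turns on one responder (5/22 against 6/22), and the exact 95% interval is between about 15 and 40 points wide for counts from 0 to 6.

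The threshold, p-value and interval figures need only the protocol's nulls and sample sizes. The 24% multiplicity figure also needs independence, maximum cohort sizes and the 30/52 split. Confidence is medium, because the shells, protocol v10.0 and two SAP sections cannot be read. This is worth fixing, but it does not call for redesign.

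**What to change.** 1. In SAP 15.1 and the response tables, give for each expansion cohort and dosing regimen, in the FAS, the one-sided exact binomial p-value against the protocol null and the two-sided 95% Clopper-Pearson interval. Put confirmed response first and unconfirmed as supportive.
2. Data to 22 March 2021 have already been reported under SAP v4 (SAP addendum 2.1), and the addendum does not repeat the response tables. The practical place is therefore an added output in the CSR addendum, identified as implementing protocol 10.2.3.
3. Footnote that the one-sided 5% test matches the two-sided 90% interval. For example, 7/22 against 15% gives p=0.037, 95% CI 13.9-54.9% and 90% CI 16.0-51.5%.
4. Label the tests exploratory and unadjusted for multiplicity, with the roughly 24% figure and its assumptions.
5. For Cohort 7, state which response definition the 15% null applies to. Protocol 10.4 assesses response "for patients with ovarian cancer according to RECIST 1.1 in combination with CA 125", and SAP 15.1 also uses the combination, but no passage ties the null to it. Show the other definition as supportive.
6. State an interval method and level for the subgroup forest plot.
7. If the test was omitted deliberately, record that with the reason in 4.9 and still report the exact intervals.

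The cost is SAP or addendum wording, one p-value and one interval per cohort and regimen in each response table, and short footnotes. No new data are needed.
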